6.3 Safety

Safety during in-person procedures: Participants will be wearing a safety harness system during the laboratory pre- and post-tests performed on motorized equipment such as the Balance Master and treadmill. For clinical tests, participants will be secured with a gait belt and will be allowed to use their assistive device (if using one) with close monitoring by the researcher or clinician. During the training sessions, the participants will also wear a gait belt, and external assistance (contact guard support) will be given for safety.

Safety during online procedures: Participants will be provided with a heart-rate, oxygen saturation and physical activity monitor which will be mailed to them after telephone screening. To further ensure safety, 2 additional steps will be followed prior to participation in the study:

- 1) If the participant's resting O2 saturations is < 90% and heart rate is >85% of age predicted maximal heart rate, they will be excluded or given the option of obtaining physician consent to be included in the study. The health coach will monitor participant's resting heart rate and O2 saturation at the beginning of every testing/training session and at regular intervals during the training.
- 2) We will remotely administer 2-min walk test (shortened version of 6 min walk test) during the online assessment session for Group 3 (online assessment and online training). In this test, participants will march in spot or around the room (with health coach able to see them on the screen) in front of the health coach for 2 minutes with the pulse oximeter on. On completion, the health coach will obtain the heart rate and oxygen saturation. If the HR exceeds 85% of age appropriate HR max and O2 saturation falls below 90% then they will be excluded from the study. For the testing procedure as well as the training procedure research personnel will engage with one participant only. During every zoom meeting, participants will not

proceed with any further testing or intervention if HR exceeds 85% of HRmax, or an increase in HR > 20 bpm of the resting HR. These measures will be recorded with the heart rate monitors sent to the participants. The tests included in the protocol were selected after a thorough discussion with 5 physical therapists who have been engaging and delivering telerehabilitation over the last 4 months of suspended inperson services. All tests are considering safe, reliability and validity of the tests and those that are easy to administer via telerehab. The remote research personnel will monitor the heart rate throughout the sessions. In addition, the test will be stopped if the remote research personnel observes any of the following signs occur during testing indicating cardiovascular intolerance: marked dyspnea, pallor, volitional fatigue, and imbalance during training. Furthermore, subjects will be asked to alert the remote research personnel and the helper buddy if they experience any discomfort such as tightness in the chest, excessive sweating, pain in chest, light headedness or dizziness, headache, and nausea. The test will be stopped if any of the above symptoms is reported by the participant during testing and training. Participants will also be required to place a sturdy chair approved by the remote research personnel in front of them for support, if needed throughout the training session. The helper buddy must be present to assist or provide physical support if needed during the procedures.

We will use an application called "Zoom" for our online screening an intervention. This zoom application will be HIPAA compliant version of 'Zoom' for all the sessions. This service includes access and authentication measure, all communications are safeguarded with end-to-end AES-256-bit encryption, and the platform integrates with the Epic electronic health record network to support healthcare workflows. Additionally, Zoom has "conduit exception" which means the application does not have access to personal health information (PHI). 'Zoom' does not have access to identifiable PHI and protects and encrypt all audio, video, and screen sharing data. Participants will only use the link provided by the research personnel, which would have: https://zoom.us/ followed by a long string of numbers, letters both capitalized and lower-case. For every testing/training session, we will be providing a new link to the participants to maintain security with only the research personnel having the rights to admit. No personal health information will be asked or recorded during these meetings.

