6.1 Participant Screening

Inclusion Criteria

- Walking speed <0.8m/s
- Self-reported Physical activity <3 hours/week
- Hand grip strength <30 kgs for men & <20 kgs for women (this will be assessed only for participants who come for in-person assessment)
- Not on any sedative drugs
- Can understand & communicate in English
- Ability to walk more than 30 feet with or without an assistive device
- Must have either a desktop computer/laptop/tablet with access to internet (only for participants who choose to go for online assessments and/or training)Must have a helper buddy assistance (only for participants who choose to go for online assessments and/or training). The helper buddy will be asked to stay in the same room throughout the online assessment and online training sessions. The helper buddy will not participate in any other way throughout the research procedures. In case of any adverse event, we will follow the adverse event protocol. The session will be immediately concluded, and the participant will be provided all the necessary support by the helper buddy while the research personnel stays online to ensure the participant is taken care of. The participant will be asked for symptoms and the type of discomfort he/she is experiencing. The adverse event will be immediately reported to the PI and the participant will be asked to visit his physician or doctor to seek medical attention in case the symptoms persist for more than a day. In case of emergency, like chest discomfort, the helper buddy will be asked to call 911 immediately
- 2-minute step in place test or walk around: The participant is asked to stand up straight next to the wall with the heart rate/O2 monitor plugged in to the index finger. The subject then marches in place or walks around the room (with health coach able to see them on the screen) for two minutes. On completion, the health coach will obtain the heart rate and oxygen saturation. If the HR exceeds 85% of age appropriate HR max and O2 saturation falls below 90% then they will be excluded from the study.

Exclusion Criteria

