- Participants will not proceed with the study if any of the following occurs at baseline measurement: 1) HR > 85% of age-predicted maximal heart rate (HRmax) (HRmax = 220 age), 2) systolic blood pressure (SBP) > 165 mmHg and/or diastolic blood pressure (DBP) > 110 mmHg during resting), and/or 3) oxygen saturation (measured by pulse oximeter) during resting < 90% (only for participants who choose to go for inperson assessment and/or training). For The blood pressure criteria is only for participants who choose to go for in-person assessment and/or training which will be measured in laboratory (Group 1 and 2). To serve good for safety in group 3 (online assessment and online training), we will mail O₂ saturation monitors along with heart rate monitors. Participants will not proceed with the study if at baseline measurement HR > 85% of age-predicted maximal heart rate (HRmax) (HRmax = 220 age) (only for participants who choose to go for online assessments and/or training). If excluded and the participant wants to participate in the study, they would need to obtain a physician consent.
- Unable to stand for 5 minutes without an assistive device (length of a Wii Fit game)
- Uncontrolled acute medical/surgical, neurological or cardiovascular disease
- History of bone fracture or significant other systemic disease or surgery in the last six months
- Moderate to severe cognitive impairment (MOCA <24/30)
- Specific to MRI participants: Self-reported presence of pacemaker, metal implants other than orthopedic implants, and/or Claustrophobia, cataract surgery (lens not compatible to the MRI confirmed by the MRI technician)
- Do not have either a desktop computer/laptop/tablet with access to internet (only for participants who choose to go for online assessments and/or training)
- Do not have a helper buddy to assist or provide physical support (only for participants who choose to go for online assessments and/or training)
- Participants who cannot understand and communicate in English will be excluded due to instructions for training and protocol being provided in English.

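### In Group 3 (online), no numeric entry rule excludes on low oxygen saturation alone: each saturation rule also requires a high heart rate

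*Combined protocol and SAP*

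**What the plan says.** **Entry, online.** Step 1 of the online procedures in section 6.3 applies at rest. A person is excluded, or offered the physician-consent route, if "resting O2 saturations is < 90% and heart rate is >85% of age predicted maximal heart rate". For the 2-minute test, section 6.1 (Inclusion Criteria) says "If the HR exceeds 85% of age appropriate HR max and O2 saturation falls below 90% then they will be excluded from the study", and 6.3 step 2 repeats this for Group 3.

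**Entry, in person.** Section 6.1 (Exclusion Criteria) lists heart rate, blood pressure and saturation as alternatives, ending "and/or 3) oxygen saturation (measured by pulse oximeter) during resting < 90% (only for participants who choose to go for inperson assessment and/or training". Here low saturation excludes by itself, but the bracket removes Group 3.

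**Entry, the online sentence in 6.1.** For safety, Group 3 is mailed "saturation monitors along with heart rate monitors". The rule that follows for online participants is "Participants will not proceed with the study if at baseline measurement HR > 85% of age-predicted maximal heart rate", with no saturation term. The paragraph closes with "If excluded and the participant wants to participate in the study, they would need to obtain a physician consent".

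**During online sessions.** Section 6.3 has the health coach check "resting heart rate and O2 saturation at the beginning of every testing/training session" and at intervals during training. The numeric limits it gives are "if HR exceeds 85% of HRmax, or an increase in HR > 20 bpm of the resting HR". It also stops for observed signs (such as marked dyspnea, pallor or imbalance) and for reported symptoms (such as chest pain or dizziness). It gives no saturation value for stopping.

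**Section 11.0** does contain a stop value, blood oxygen below 92%. It names no group and describes a laboratory setting.

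**The concern.** Saturation is measured at entry in Group 3, but the result cannot change the numeric decision. Either heart rate is already above its limit, in which case the online sentence in 6.1 excludes the person anyway, or it is not, in which case the saturation reading is ignored.

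At stake is participant safety. A frail adult with a resting saturation below 90% would be held for a physician's decision in Groups 1 and 2. In Group 3 the same person goes forward without that step, in the setting where the coach is on a screen and only a helper is in the room. The session rules in 6.3 do not clearly make up for this, because the coach is told to read saturation but not what value to act on.

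**Working it through.** The plan gives no figure for this point, and the sample-size numbers in section 12.0 do not enter. The check is of logic and thresholds.

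**Definitions.** S = saturation below 90%. H = heart rate above 85% of age-predicted maximum, where the maximum is 220 − age (section 6.1).

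**Rules at rest, before blood pressure.**
- In person (6.1): exclude if H or S.
- Online, 6.3 step 1: exclude if S and H.
- Online, 6.1: exclude if H.
- Group 3 overall: H or (S and H), which reduces to H.

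| Saturation <90% (S) | HR >85% of maximum (H) | In-person rule | 6.3 step 1 alone | All Group 3 rules |
|---|---|---|---|---|
| no | no | passes | passes | passes |
| no | yes | excluded | passes | excluded |
| yes | no | excluded | passes | **passes** |
| yes | yes | excluded | excluded | excluded |

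Excluded combinations: 3 of 4 in person, 1 of 4 under 6.3 step 1, 2 of 4 under all Group 3 rules. The in-person and Group 3 outcomes differ only in the third row. Exclusion at rest is subject to the physician-consent route throughout.

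**Heart rate needed before the saturation clause acts:** 0.85 × (220 − age).
- Age 60: 0.85 × 160 = 136 bpm
- Age 70: 0.85 × 150 = 127.5 bpm
- Age 80: 0.85 × 140 = 119 bpm
- Age 90: 0.85 × 130 = 110.5 bpm

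To illustrate with hypothetical values, a 70-year-old with saturation 85% and resting heart rate 80 has S true and H false (80 < 127.5). That person passes in Group 3 and needs physician consent in Groups 1 and 2.

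**After the 2-minute test.** The rule is again S and H, so a fall below 90% with heart rate at or under the limit does not exclude.

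**Effect of replacing 'and' by 'or'.** At rest only the third row changes, because 6.1 already excludes online participants on heart rate alone. In the 2-minute rule two rows change: low saturation alone and high heart rate alone both become exclusions. The second is in line with 6.2 (TeleXercise) and 6.3, which already bar continuing above 85% of maximum.

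**Section 11.0.** The 92% stop can be parsed in two ways: (discomfort and raised heart rate) or low oxygen or raised blood pressure; or discomfort together with any one of the others. Whether it covers Zoom sessions is also open. Readings of 90% and 91% satisfy the 90% entry limit and lie below 92%. Whether that matters depends on which parsing is meant and on whether a stable resting value counts as a drop.

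**The case against.** The strongest reply is that this is a drafting slip. Taken literally, the saturation clause in 6.3 does nothing at rest, and oximeters are mailed to Group 3 for safety. Section 6.1 then separately says that the blood pressure limits are in-person only, which would be redundant if saturation were already meant to be in-person only. An 'either' reading reconciles 6.1 with 6.3. That is probably what was intended, but staff follow the written rule, and the conjunction appears three times across two sections. A probable slip in a safety rule still has to be corrected.

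A second reply is that other safeguards exist: the coach's saturation checks, the sign and symptom stops in 6.3, the helper, the emergency-call instruction in 6.1 and the medical-history exclusions. These stand and reduce the hazard. They do not supply a saturation limit.

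A reader might go further in four ways that the documents do not support:
- That every Group 3 entry rule needs both conditions. Heart rate alone excludes under 6.1; only the rules that use saturation need both.
- That such a person would be randomised. Section 6.0 does not fix when the coin is flipped relative to baseline testing.
- That people at 90–91% would be admitted and then stopped before starting. This depends on one reading of 11.0.
- That the fatigue rule in 7.0 will cost a predictable number of participants. No rate is given, and Figure 2, the adverse event protocol, is not shown and may grade the response.

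**Conclusion.** The point holds and should be fixed before Group 3 enrols under this text. One of the four resting combinations, saturation below 90% with heart rate not above 85% of maximum, is excluded in person (absent physician consent) and passes in Group 3. The same gap exists after the 2-minute test. The gap is specific to Group 3, because Group 2 has in-person assessment and falls under the stand-alone limit. The conclusion rests on reading 'and' and the in-person bracket as written. The number of people affected is unknown.

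During online sessions, 6.3 states no saturation stop value, and 11.0 is too unclear in scope and logic to fill that place with confidence. The 90–91% overlap is only a reason to clarify 11.0.

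A separate, lesser inconsistency concerns fatigue. Section 7.0 (online risks, item 5) discontinues Group 2 and 3 participants from the study for fatigue without grading it, although item 2 lists some fatigue as a risk of the online tests and training. Section 6.2 (TeleXercise) answers fatigue with a seated rest. Subject to Figure 2, the two need reconciling.

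**What to change.** Amend the safety text:

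1. **6.3 step 1:** replace 'and' by 'or'.
2. **6.1, online sentence:** add resting saturation below 90% for Group 3, with the existing physician-consent route.
3. **2-minute rule (6.1 and 6.3 step 2):** make saturation below 90% sufficient on its own. If 'or' is used, state that heart rate above 85% of maximum after the test then also excludes by itself.
4. **6.3, session limits:** give a saturation stop value for Zoom sessions.
5. **11.0:** say whether the stop rule applies online, whether discomfort is also required, and how the 92% value relates to the 90% entry limit.
6. **Lower priority, 7.0 item 5:** align with the seated rest in 6.2 and with Figure 2, and state that stopping training does not end outcome collection.

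The cost is a short protocol amendment. It adds no participants, visits or procedures, and the oximeters are already being mailed. Some Group 3 applicants will newly need physician consent or be excluded; their number cannot be estimated from the documents.

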Preventing falls during training sessions: There is also a risk of balance loss and falls while participating in the actual balance training on the Wii-Fit balance board. For that reason, participants will always be made to wear gait belt and supervised by a research personnel mentioned in Appendix P during the training sessions. Blood pressure and heart rate will be monitored prior to the training session, after each sub-session (completion of 4 games). Participants will be given a chair to sit back after each subsession (completion of 4 games - approximately 10 minutes considering each game played for 1.5 minutes) or if he/she feels tired during the game (i.e., ≥ 15 on Borg scale for perceived exertion) or if the blood pressure is beyond normal limits (i.e. > 85% of age-predicted maximal heart rate). More than or equal to 15 on the Borg scale of perceived exertion indicates that the intensity of the physical activity performed was high and that it gives an idea to the research personnel that the participant would need to slow his movements down. Additionally, if at any point the heart rate, blood pressure, drops or rises above the pre-determined acceptable limits, the session will be terminated. Participants will be asked to inform the experimenter about any of the symptoms including marked breathlessness, excessive sweating, pain in chest, or fatigue. The research personnel will observe for any changes in participant's facial expression indicating anxiety or discomfort. In case of any discomfort, the session will be terminated, and the time of the training session will be noted.

Preventing injuries from training: The proposed setup incorporates several precautionary features, evolved through a decade of research, against such injuries. To further reduce the risk of injury, all Participants will undergo a series of stretching and warm-up exercises at the start of the experiment and training. A physical therapist or an exercise specialist on the team will conduct these procedures. Stretches will encompass all major muscle groups of the lower limbs and trunk. Warm-ups include activities such as walking, lunges, squats, high stepping and chair rise.

Potential Risks: Pertaining Online assessment and training

Clinical test related risks

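### Two safety rules fail as written: low oxygen saturation alone never excludes a Group 3 participant at entry, and a blood-pressure limit is given as a heart-rate figure

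*Combined protocol and SAP*

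**What the plan says.** **Saturation at entry.** The plan has three relevant rules.

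- Section 6.3, online procedures, at rest: if the participant's "resting O2 saturations is < 90% and heart rate is >85% of age predicted maximal heart rate, they will be excluded", or offered the option of physician consent.
- Section 6.1, 2-minute step or walk test: "If the HR exceeds 85% of age appropriate HR max and O2 saturation falls below 90" per cent, the person is excluded. Section 6.3 repeats this for Group 3 with the same conjunction.
- Section 6.1, Exclusion Criteria: a list of baseline limits joined by *and/or*, one of which is "oxygen saturation (measured by pulse oximeter) during resting < 90% (only for participants who choose to go for inperson assessment and/or training"). For online participants the sentence reads "Participants will not proceed with the study if at baseline measurement HR > 85% of age-predicted maximal heart rate (HRmax"), with no saturation term. The list closes with "If excluded and the participant wants to participate in the study, they would need to obtain a physician consent".

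**Saturation during sessions.** Section 6.3 has the health coach check resting heart rate and saturation at the start of every online session and at intervals during training. It gives no saturation value that calls for action. Its numerical bar on going further is on heart rate: no more testing or "intervention if HR exceeds 85% of HRmax, or an increase in HR > 20 bpm of the resting HR". Symptoms also stop a session. Section 11.0 has a stop for saturation under 92%.

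**Blood pressure in training.** Section 7.0, on preventing falls in Wii-Fit training, seats the participant "if the blood pressure is beyond normal limits (i.e. > 85% of age-predicted maximal heart rate"). The next tier is "if at any point the heart rate, blood pressure, drops or rises above the pre-determined acceptable limits, the session will be terminated", and those limits are not stated there. Section 11.0 gives stop values of more than 20 mmHg systolic or 15 mmHg diastolic above rest.

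**The concern.** A rule that needs two abnormal readings before it acts is weaker than either reading alone. Here the second reading, a resting heart rate above 85% of the age-predicted maximum, is so extreme that the saturation limit can hardly come into play. Group 3 is also the group with the least direct supervision: frail adults who exercise at home over Zoom with a helper in the room. Followed literally, a Group 3 volunteer with low saturation, an ordinary heart rate and no symptoms is enrolled and is never referred to a physician. The same readings would exclude a Group 1 or Group 2 volunteer.

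The Section 7.0 rule has a different fault. Staff told to seat a participant when blood pressure passes a fraction of maximal heart rate have no blood-pressure value to compare with.

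**Working it through.** **Planned numbers.** Enrolled 120, attrition 20%: 120 × 0.8 = 96 analysed, and 96 / 6 = 16 per subgroup, as Section 12.0 states. Group 3 has two subgroups, so 2 × 16 = 32 analysed. Enrolled: 16 / 0.8 = 20 per subgroup, 2 × 20 = 40. Both figures assume equal subgroups, although participants choose Group 1, 2 or 3 themselves.

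**Heart rate needed before saturation counts.** Section 6.1 uses HRmax = 220 − age. The limit is 0.85 × (220 − age).

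| Age | HRmax | 85% limit (bpm) |
|---|---|---|
| 60 | 160 | 136 |
| 75 | 145 | 123.25 |
| 80 | 140 | 119 |
| 85 | 135 | 114.75 |

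**Resting decision for each pair of readings**, from Sections 6.1 and 6.3:

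| Saturation | Resting heart rate | Groups 1 and 2 | Group 3 |
|---|---|---|---|
| < 90% | > 85% HRmax | excluded | excluded |
| < 90% | ≤ 85% HRmax | excluded | **passes** |
| ≥ 90% | > 85% HRmax | excluded | excluded |
| ≥ 90% | ≤ 85% HRmax | passes | passes |

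In Group 3 the outcome depends on heart rate alone. Everyone who meets both parts of the Section 6.3 resting rule already meets the heart-rate exclusion in Section 6.1, so the saturation term adds no exclusions. For example, at age 75 with assumed resting readings of 85% saturation and 80 bpm, the heart-rate limit is 123.25 bpm. A Group 3 volunteer passes and a Group 1 or 2 volunteer does not.

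**After the march.** Exclusion again needs both readings, so a fall below 90% with heart rate at or under the limit does not exclude.

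**Blood-pressure limit.** The quantity in Section 7.0 is in beats per minute. Reading the number as mmHg does not rescue it: at ages 60 and 75 it would be 136 and 123, while Section 6.1 admits in-person participants with resting systolic pressure up to 165 mmHg. Some would be over that limit before starting to play.

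**The case against.** The strongest reply is that the conjunction is a slip and the intent is clear. Saturation monitors are mailed to Group 3 expressly for safety, and a saturation term that changes no decision cannot have been meant. The coach sees saturation before every session, so low values would not go unnoticed. Uncontrolled cardiovascular disease is excluded, symptoms stop a session, and the helper has instructions for emergencies. The adverse event figure is not available to us and may say more. For blood pressure, Section 11.0 has a working stop rule in mmHg that covers in-person training. Even corrected, the resting rule only adds a referral, because physician consent can reverse it.

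Much of this stands, and it limits the seriousness. It does not remove the fault. The conjunction appears three times, so staff following the text have no reason to read it as *or*. The per-session check carries no action value. The 92% stop applies by its wording to testing and training sessions, but its surroundings are those of the laboratory (two people in the area, blood pressure readings, a defibrillator), and it does not mention Zoom.

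A reader might go further in three directions that the documents do not support.

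- *The online heart-rate limits conflict.* Section 6.3 bars proceeding above 85% of HRmax or more than 20 bpm above rest, while Section 6.2 names only the 85% limit. Staff can obey both by using the stricter, and the 85% condition in Section 6.2 is necessary, not sufficient. No heart-rate responses are given, so an effect on the step test or training dose is not shown.
- *Section 11.0 would stop the cycle test at 20 bpm above rest.* Its unpunctuated list can be read as requiring discomfort together with that rise, so the conflict is not established.
- *The entry floor should be 92% in every group.* An entry limit and an in-session stop need not be equal. That is a clinical choice, and the 90% limit for Groups 1 and 2 is usable as it stands.

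**Conclusion.** Both rules are wrong as written. In Group 3, saturation below 90% alone neither excludes at entry nor triggers physician consent, and this follows from the wording without any assumption about heart rates. The Section 7.0 blood-pressure trigger cannot be applied. It is probably a mislabelled heart-rate limit.

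Severity is minor to moderate. The saturation gap is at entry and concerns a planned 40 or so enrolled participants, on the assumption of equal subgroups. The documents do not allow an estimate of how many would have low saturation and an ordinary heart rate. A reader might infer that low saturation would go unseen in Group 3 or that the trial's results are at risk. The first is contradicted by the check at each session, and nothing in the plan shows the second.

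**What to change.** 1. In Section 6.1 (2-minute test) and Section 6.3 (resting rule and march), replace *and* with *or*. Saturation below 90% alone then leads to exclusion in Group 3 or, at rest, to physician consent, in line with Groups 1 and 2. The same edit makes heart rate above 85% of HRmax after the march an exclusion by itself, which agrees with the Section 6.3 bar on proceeding above that limit.
2. State in Section 11.0 that the stop at saturation under 92% applies to Zoom sessions.
3. In Section 7.0, label the 85% figure as a heart-rate limit. Use the Section 11.0 values, a rise of more than 20 mmHg systolic or 15 mmHg diastolic above rest, as the blood-pressure limit. Section 11.0 already stops the session at these values, so a separate, lower seat-and-rest value would be for the investigators to set.

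The cost is a text amendment and an instruction to staff. The monitors are already supplied, so no procedure is added. A few more Group 3 volunteers may be excluded or need physician consent.
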